- Incidence, nature, severity and seriousness of observed adverse events and adverse device events in the 6 months following implantation.
- Incidence, nature, severity and seriousness of observed adverse events and adverse device events in the 12 months following implantation.

Performance

- Limits of agreement between measurements made using GAT and the ARGOS-IO system from V05 (day 30) through V11 (day 360).
- Performance of the ARGOS-IO system after 6 months by means of incidence of observed device malfunctions.
- Performance of the ARGOS-IO system after 12 months by means of incidence of observed device malfunctions.
- User acceptance of the implantation procedure by means of evaluation of implantation procedure questionnaires (investigators).
- User acceptance of the ARGOS-IO system at the investigational site by means of evaluation of investigator acceptance questionnaires (investigators).
- User acceptance of the ARGOS-IO system at home by means of evaluation of patient acceptance questionnaires (patients).
- Daily IOP self-measurement profiles (patients).

Definition of the analysis populations

The safety population comprises all subjects for whom ARGOS-IO pressure sensor implantation was attempted, whether or not the implantation was successful. In this clinical investigation the intention-to-treat (ITT) population comprises the same subjects as defined in the safety population.

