8. DESIGN OF THE CLINICAL INVESTIGATION

8.1 General Aspects

8.1.1 Description of the type of clinical investigation

The trial will be conducted as an open, prospective, multicenter single-arm clinical trial using the two-stage design described by Simon (Simon, 1989). In the first stage, 11 patients will have an ARGOS-IO pressure sensor implanted, after which enrollment will be halted until the patients have completed their 3 months follow-up visits and an interim analysis has been performed. The interim analysis will be reviewed by the DSMB. If two or more of these 11 patients in the first stage are found to have had an SADE, further enrollment into the study will be stopped. If not, enrollment will resume until another 11 patients have had an ARGOS-IO pressure sensor implanted. If two or fewer of the total 22 patients experience an SADE, a conclusion for safety will be made at the 5% significance level. A corresponding 95% confidence interval for the SADE rate will be calculated according to the procedure of Koyoma (2008).

 Implandata Ophthalmic Products GmbH	Clinical Investigation Plan ARGOS-02	Revision C
		Page 60 of 106

All patients who receive an ARGOS-IO implant will return for 10 follow-up visits to the clinic (day 1, 3, 10, 30, 60, 90, 120, 180, 240, 360) during the 12-month post-surgical period (see Table 6: Assessment Schedule). To allow comparison of the IOP measurement methods, IOP measurements will be made at every visit with GAT and with the ARGOS-IO systems beginning at V5 (day 30).

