9.2 Sample Size Calculation

The sample size calculation was based on the study's purpose of establishing safety.

To minimize the required sample size and consequently the number of patients exposed to risk while at the same time maximizing the chances of detecting safety events, a two-stage design based on the rate of non-events was chosen (Simon, 1989). The event of interest was defined as a serious device-related adverse events (SADEs). Based on a probability of non-events of $p_0=0.75$ for the first stage and an overall acceptable probability of $p_1=0.94$, a sample size of at least 11 evaluable patients in the first stage and additional 11 patients in the second stage are required. This maintains a type 1 error probability of 5% and the power of 80% based on minimizing the maximal sample size and results in an expected sample size of 13.2 patients.

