9.11 Datasets to be analyzed

9.11.1 Safety population

The data of all patients, with successful implantation of the ARGOS-IO implant, will be used for the safety evaluation.

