9.11.2 The Full-Analysis-Set (FAS) population

The FAS population comprises all subjects in whom an ARGOS-IO pressure sensor was successfully implanted. Measurements recorded by the patient will not be included into the evaluation of the FAS population. Additional information about the drop-outs: all patients who revoke their consent and agreement preoperatively will be regarded as screen failures and will not be included in the statistical evaluation. All patients who revoke their consent and agreement postoperatively will be considered withdrawals and their data will be evaluated in the safety analysis.

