4.1 Analysis Populations

Within the framework of this study, the following two main populations are analysed:

- **Safety Population:** consists of all patients with attempted implantation of the ARGOS-IO implant, whether or not successful.
- **Full Analysis Set (FAS):** The FAS population comprises all subjects in whom an ARGOS-IO pressure sensor was successfully implanted. Measurements recorded by the patient will not

be included into the evaluation of the FAS population. Additional information about the drop-outs: all patients who revoke their consent and agreement preoperatively will be regarded as screen failures and will not be included in the statistical evaluation. All patients who revoke their consent and agreement postoperatively will be considered withdrawals and their data will be evaluated in the safety analysis.

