7.2 Evaluation of Primary Safety Variables

Incidence of SADEs in the 3 month period immediately following implantation will be assessed. The decision on safety follows the rule of Simon's optimal two-stage design (parameters: $\alpha=0.05$, $\beta=0.20$, $p_0 = 0.75$, $p_1 = 0.94$). A corresponding 95% confidence interval will be given for the portion of SADEs within the safety population. The confidence interval for the SADE rate will be calculated using the method proposed by Koyama (Koyama & Chen, 2008). These calculations will be based on the number of patients experiencing a SADE based on the safety population. If the obtained confidence interval does not include any value lower than 0.94, it can be concluded that the SADE rate is at most 6%.

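### CIP 9.11.1 restricts the safety population to successful implantations, while the CIP synopsis and SAP 4.1 include every attempt; on the supplied text a SADE at a failed attempt could be left out of the primary count

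*Protocol*

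**What the plan says.** Three passages define the safety population, and they do not agree.

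- CIP synopsis, in the row on data analysis and statistics: "The safety population comprises all subjects for whom ARGOS-IO pressure sensor implantation was attempted, whether or not the implantation was successful". The ITT population is declared to be the same set.
- CIP 9.11.1: "The data of all patients, with successful implantation of the ARGOS-IO implant, will be used for the safety evaluation".
- SAP 4.1: the safety population "consists of all patients with attempted implantation of the ARGOS-IO implant, whether or not successful".

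The CIP 9.11.1 set is the same as the full analysis set of CIP 9.11.2: "The FAS population comprises all subjects in whom an ARGOS-IO pressure sensor was successfully implanted".

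The primary result depends on this population. The CIP synopsis and CIP 9.1 (also as amended by the addendum) place the SADE proportion and its confidence interval in the safety population. SAP 7.2 does the same: "These calculations will be based on the number of patients experiencing a SADE based on the safety population".

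The final rule in CIP 8.1.1, kept by the addendum, is: "If two or fewer of the total 22 patients experience an SADE, a conclusion for safety will be made at the 5% significance level". The stage-1 stop in CIP 8.1.1 applies "If two or more of these 11 patients in the first stage are found to have had an SADE". The addendum drops that stop, and SAP 2.10 and 8.1 keep it.

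Failed attempts are foreseen. The synopsis and CIP 8.5.2 let the surgeon stop the sensor implantation during surgery, CIP 8.3.3.3 lists this as a withdrawal reason, and SAP 4.2 plans a subgroup by successful implantation.

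**The concern.** The injector and the implantation step are part of what is being tested, and CIP 6.3 lists surgical implantation first among the anticipated risks. A SADE that occurs while an attempt fails would meet the event definition. Under CIP 9.11.1 it could still fall outside the analysed set because the attempt failed.

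The limits are 1 patient in the first 11 and 2 in 22, so a single patient can decide the conclusion. Neither the visible addendum nor SAP 8.2 (changes in the planned analysis) mentions the population definition, so nothing supplied resolves the conflict explicitly.

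**Working it through.** **Inputs.** Stage 1 has 11 patients with at most 1 SADE patient allowed; overall there are 22 with at most 2 allowed (CIP 9.1, SAP Table 2). The SADE rates are 0.25, from "a probability of non-events of $p_0=0.75$ for the first stage", and 0.06, from p1 = 0.94 (CIP 9.2). CIP 9.5 gives a stricter limit (fewer than two). That is a separate matter, and the limit of two is used here.

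**Reproducing the plan.** X1 and X2 are the SADE patients in each group of 11. P(conclude safety) = P(X1=0)·P(X2≤2) + P(X1=1)·P(X2≤1).

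- Rate 0.25: 0.0422 × 0.4552 + 0.1549 × 0.1971 = 0.0497. Expected N = 11 + 0.1971 × 11 = 13.17.
- Rate 0.06: 0.5063 × 0.9752 + 0.3555 × 0.8618 = 0.800.

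These match the stated 5%, 80% and 13.2.

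**When one excluded SADE matters at the final decision.** The implanted patients must have exactly 2 SADEs. Counting the failed attempt then gives 3, which fails.

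- Rule of at most 2 in 22 alone, rate 0.06: P(X=2) = 231 × 0.06² × 0.94²⁰ = 231 × 0.0036 × 0.2901 = 0.241. At rate 0.25 it is 0.046.
- With the stage-1 limit as well, remove the path with both SADEs in stage 1: P(X1=2)·P(X2=0) = 0.1134 × 0.5063 = 0.057. The result is 0.241 − 0.057 = 0.184.

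Both figures are conditional on a failed attempt with a SADE. As an illustration, assume exactly one failed attempt in addition to the 22 implanted patients, with SADE probability f. The chance of reversal under the first rule at 6% is 0.241 × f: 0.060 for f = 0.25, 0.121 for f = 0.5, and 0.241 for f = 1.

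**If the event falls in stage 1.** Assume the failed attempt has a SADE and takes one of the first 11 places. Passing then needs 0 SADEs in the other 10 and at most 1 in the next 11: 0.94¹⁰ × 0.8618 = 0.5386 × 0.8618 = 0.464, against 0.800 if the patient is excluded and replaced. The chance of a stage-1 stop is 1 − 0.5386 = 0.461, against 0.138.

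**Direction of the effect on the rate.** Start from 2/22 = 9.1%. Adding a failed attempt with a SADE gives 3/23 = 13.0%; adding one without gives 2/23 = 8.7%. The direction depends on the SADE risk in failed attempts, which is not given.

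**Does the rule fit the attempted set?** CIP 9.1 counts the 22 as patients who received implants, and CIP 8.1.5 replaces those withdrawn up to implant. The attempted set can therefore exceed 22. If the limit stays at 2, the single-stage type I error and power move from 0.0606 and 0.8576 (n = 22) to 0.0492 and 0.8431 (n = 23) and to 0.0321 and 0.8129 (n = 25), taking the same SADE rate for every attempt. SAP 5.2 recalculates the critical value only for losses after implantation.

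**The case against.** The SAP already uses the attempted definition, agrees with the synopsis, and is finalised before hard lock, so the planned analysis would most likely count such a patient. The SAP cites CIP Rev. G, whereas the supplied CIP is Rev. C with an addendum whose text breaks off, so CIP 9.11.1 may since have been corrected. CIP 8.3.3.3 and SAP 2.6 say that data up to withdrawal enter the safety analysis and list infeasibility found during surgery as a withdrawal reason. That arguably brings an abandoned attempt in, although the sentence follows text on drop-outs after implantation. Nor would the event go unseen: AEs are collected at the surgery visit, and under the addendum any SADE halts enrolment and calls the DSMB.

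All of this stands, and it rules out three stronger readings. A reader might infer that the primary analysis is undetermined; the SAP makes one reading much more likely. A reader might infer that CIP 9.11.1 necessarily biases the SADE rate downward; it can only lower the count, and the rate can move either way. A reader might also infer that about one trial in five would be reversed; the documents do not support this, because 0.24 and 0.18 hold only once a failed attempt with a SADE has happened.

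What the objection does not remove is the conflict itself. The SAP describes itself as elaborating the CIP, and the CIP's own section on analysis sets gives a different set from its synopsis.

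**Conclusion.** The contradiction is real and reaches the primary safety decision, but its practical weight is moderate. On the supplied text, a SADE at a failed or abandoned attempt could be left out of the primary count, although the SAP definition would probably prevent this.

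If such an event occurs and is excluded, the final decision could be reversed when the implanted patients have exactly 2 SADEs: probability 0.24 at a 6% rate, or 0.18 with the stage-1 limit also met. The second figure assumes that the event does not itself alter the stage-1 count; an event in stage 1 can matter more, as the illustration shows. The calculations assume independent patients with a common SADE rate. No unconditional size can be given without the frequency of failed attempts and their SADE risk. CIP Rev. G should be checked first.

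**What to change.** 1. Replace the text of CIP 9.11.1 with the synopsis and SAP 4.1 definition (all attempted implantations). State that the primary SADE count, the stage-1 count and the AE tables use this set. SAP 7.4 calls the set for the AE tables the safety evaluation set, a name that SAP 4.1 does not define.
2. State whether a failed attempt takes one of the 22 (and first 11) places or is replaced. If it is replaced, extend SAP 5.2 so that the critical value is recalculated when the attempted set exceeds 22.
3. Reconcile the start of AE/SADE recording, which is implantation in CIP 8.4.4.5 and 11.1.4 but the point of surgery in CIP 11.1.3, so that events during a failed attempt are captured.

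The cost is a few sentences. The SADE count may be slightly less favourable. There is also a data gap to acknowledge: CIP 8.1.1 schedules the follow-up visits only for patients who receive an implant, so failed attempts have no planned 3-month assessment. The plan should say how their endpoint status is established.

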2. ABBREVIATIONS AND DEFINITIONS

Abbreviation	Definition
α	Type I error
ACA	Anterior Chamber Angle
ACD	Anterior Chamber Depth
ADE	Adverse Device Event
AE	Adverse Event
AS	Anterior Segment
ASADE	Anticipated serious adverse device effect
ASIC	Application specific integrated circuit
β	Type II error
Beta-hCG	Beta-subunit of human chorionic gonadotropin
BfArM	Bundesinstitut für Arzneimittel und Medizinprodukte
C	Celsius
CA	Competent Authority
CIP	Clinical Investigation Plan
CRA	Clinical Research Associate
CRF	Case Report Form
D	Day
dB	Decibel
DCT	Dynamic contour tonometry
DSMB	Data Safety Monitoring Board
EC	Ethics Committee
EEPROM	Electrically erasable programmable read-only memory
ETDRS	Early Treatment Diabetic Retinopathy Study
EtO	Ethylene oxide
FAS	Full-analysis-set
GAT	Goldmann Applanation Tonometry
GCP	Good Clinical Practice
GDD	Glaucoma Drainage Device
HPG	High pressure glaucoma
IB	Investigator's Brochure
ICD	Implantable Cardioverter Defibrillator
ICH	International Conference on Harmonisation
IFU	Instruction for Use

IO	Intraocular
IOL	Intraocular lens
IOP	Intraocular Pressure
ISF	Investigator Site File
ISO	International Organization for Standardization
ITT	Intention to treat
KPro	Keratoprosthesis
LAL	Limulus amoebocyte lysate
MD	Macular degeneration
MHz	Megahertz
Mm	Millimeter
mmHg	millimeter(s) of mercury (a unit of pressure equal to the pressure that can support a column of mercury 1 millimeter high)
MPG	Medizinproduktegesetz
MRI	Magnetic resonance imaging
N	Sample number
NCT	Non-contact tonometry
ND:YAG	Neodymium doped yttrium aluminum garnet
OCT	Optical coherence tomography
OH	Ocular hypertension
P	Pressure
p ₀	Proportion of patients in stage 1 with positive outcome
p ₁	Proportion of patients overall with positive outcome
PIC	Patient informed consent
POAG	Primary open angle glaucoma
PS	Posterior Segment
Rev.	Revision
SADE	Serious Adverse Device Effect
SAE	Serious Adverse Event
SAP	Statistical Analysis Plan
SEM	Scanning electron microscope
SDV	Source Data Verification
T	Tesla
TMF	Trial Master File
V	Visit
VA	Visual acuity

 Implanata Ophthalmic Products GmbH	Clinical Investigation Plan ARGOS-02	Revision C
		Page 28 of 106

USADE Unanticipated serious adverse device effect
WTW White-to-white

 Implandata Ophthalmic Products GmbH	Clinical Investigation Plan ARGOS-02	Revision C <hr/> Page 29 of 106
--	---	------------------------------------

3. BACKGROUND INFORMATION

3.1 Glaucoma

An estimated 1 in 40 adults over the age of 40 has glaucoma, a group of conditions that result in damage to the optic nerve head, is characterized by a progressive thinning of the retinal nerve fiber layer and the neuroretinal rim that appears as a central depression in the optic disc. It leads to loss of visual field and if not controlled eventually to blindness, of which it is the second most common cause worldwide (Quigley, 2011) (Mansouri & Shaarawy, 2011) (King, 2013). There are two types of primary glaucoma. In primary open angle glaucoma (POAG), which accounts for approximately 70% of the glaucoma cases seen, aqueous outflow from the eye is restricted, possibly due to increased resistance in the trabecular meshwork. In closed angle glaucoma, ocular tissue, usually the iris, obstructs the drainage pathway (King, 2013).

3.2 Glaucoma Treatment

Glaucoma often remains asymptomatic until late in the disease, when irreversible vision problems become evident. Although it may be present with normal intraocular pressures (IOP), the higher the IOP, the more rapidly the damage progresses (Quigley, 2011). Reduction of IOP is the only known treatment, the main goal of which is the prevention of visual disability in the patient's lifetime (King, 2013). Lowering the IOP of patients with POAG by 20 to 40% can halve the rate of progressive damage (Quigley, 2011).

IOP reducing treatments generally begin with eye drops containing prostaglandin analogues or β -adrenergic antagonists, although as in other chronic asymptomatic diseases, patient adherence to treatment is often poor. If eye drops do not satisfactorily reduce IOP, surgical methods such as laser trabeculoplasty or trabeculectomy to reduce production of intraocular fluid, or insertion of an artificial shunt into the anterior chamber to increase its drainage may be used (Quigley, 2011)

3.3 Measurement of IOP

3.3.1 Principle and Gold Standard

Glaucoma generally develops slowly, with no obvious symptoms. For this reason the only way to determine if treatment is working is to monitor IOP regularly. The only method currently available to measure IOP directly requires the insertion of a large gauge needle into the eye and is rarely if ever used. Under normal clinical conditions, IOP is determined indirectly with one of numerous available

	Clinical Investigation Plan ARGOS-02	Revision C
		Page 30 of 106

tonometer devices. Most of these are based on the Imbert-Fick principle that the force needed to flatten a defined area of a sphere is proportional to the pressure inside the sphere resisting the deformation (Frampton, 2012), (Kakaday, Hewitt, Voelcker, Li, & Craig, 2009).

3.3.2 Available Devices

A number of different tonometric devices are available. These can be categorized based on whether or not they involve direct corneal contact.

3.3.2.1 Direct Tonometers

The Goldmann Applanation Tonometer (GAT) was first described in the 1950's and is considered to this day to be the gold standard to which all other methods for measuring IOP are compared. It measures the force required to appanate the cornea by pressing a probe of defined area directly against it. The Perkins Tonometer is a hand-held tonometer that works on the same principles as the Goldmann Tonometer (Burr, et al., 2012).

Dynamic contour tonometry (DCT) determines IOP by measuring the force required to mold the cornea to the shape of the concave probe (Frampton, 2012), while rebound tonometers calculate it from the induction current produced when a small plastic-tipped magnetized metal probe is bounced against the cornea (Burr, et al., 2012).

The TonoPen is a hand-held portable tonometer that uses a transducer in its probe tip to measures the force required to appanate/indent the cornea, while the Ocuton S, another hand-held tonometer, requires direct contact of its prism with the cornea (Cihara, 2008).

The Sensimed Triggerfish, a new system consisting of a micro-electromechanical strain gauge embedded in a disposable silicon contact lens, an adhesive antenna and a portable recorder, allows 24 hour out-patient monitoring of changes in the diameter of the corneoscleral junction that results from changes in IOP (Mansouri & Shaarawy, 2011).

3.3.2.2 Non-contact tonometers

In non-contact (air-puff) tonometry (NCT) a rapid air pulse is used to appanate the cornea. Advantages to NCT include lack of direct contact with the eye and hence no need for anesthesia, and low/no risk of corneal abrasion or infection transmission. The probe of the Ocular Response Analyzer applies a slightly stronger force to actually indent the cornea and uses a pneumatic sensor to take two measurements, the force at which the cornea is appanated initially and the that at which it appanates

	Clinical Investigation Plan ARGOS-02	Revision C
		Page 31 of 106

as it returns to normal. The difference between these two pressures is due to the viscous damping of the cornea (Frampton, 2012).

In transpalpebral tonometry, IOP is calculated from the rebound of a free-falling rod as it hits the tarsal plate of the eyelid over the sclera (Burr, et al., 2012)

3.3.3 Limitations

The accuracy of most of these devices is limited to the degree that the secondary biometric parameters they measure are affected by factors other than IOP, such as corneal thickness (Krug, Kompa, & Schrage, 2002). The majority of the direct tonometers require use of corneal anesthetics. The greatest limitation however is that almost all of the devices are cumbersome and require skill and training to use, which in effect limits their use to the clinic /office setting.

The cost and inconvenience of the required office visits result in treatment decisions that are made based on only a few IOP measurements taken months apart. However fluctuations in IOP due to patient activity and circadian rhythm are normal. The level of imprecision in repeated IOP measurements has been estimated at +/- 5 mmHg, meaning that to be 95% certain there is any treatment effect, a difference greater than 7 mmHg must be seen between single pre- and post-treatment IOP levels (Rotchford & King, 2012). When 24 hour IOP profiles are taken, which require patients be admitted to the clinic, peak values – thought to be the most relevant for patient outcome in the long term – are seen outside of normal office hours in 80% of the cases, resulting in changes to treatment (Liang, Lee, & Shields, 2009) (Mansouri & Shaarawy, 2011).

For these reasons, alternative methods are being sought that would allow more frequent IOP assessments in the home setting.

According to company information, Sensimed Triggerfish measures a “profile of 24h ocular dimensional changes”, displayed in [arbitrary units], rather than changes in IOP in [mmHg]. To date, it is unknown how the measured changes in corneal curvature relate to IOP, especially in magnitude.

